2.3. Description of participants

Purpose: To describe the patient population by intervention group.

Methods/Approach: Construct “table 1” describing the baseline characteristics of each intervention group including:

- Demographic characteristics
- Baseline medical history, Tobacco/Alcohol Information, Insurance Status, Transportation Status, Social Cognitive Theory Measures, medication history, medication adherence
- Baseline values of primary and/or secondary outcome variables: BP, PCP Attendance

Means and standard deviations will describe continuous variables, frequencies and counts will describe categorical variables. Significance testing of baseline differences between groups will not be performed based on statistical and CONSORT recommendations.¹⁻²

Intervention Exposure: Participants receiving daily BP monitoring or healthy behavior text messaging can choose to “snooze” (stop texts for 2 weeks) or de-escalate their treatment “weekly” (stop healthy behavior text messages, move to weekly BP monitoring). Participants with weekly BP monitoring can choose to “snooze” treatment (stop texts for 2 weeks) or escalate their treatment “daily” (daily BP monitoring no change to healthy behavior text messaging). The number and percentage of participants who “snooze” BP monitoring and healthy behavior texts, both daily and weekly, will be reported separately. The number and percentage of participants who choose to de-escalate from daily BP monitoring and healthy behavior texts will be reported separately as well the number and percentage who escalate their treatment. The proportion of all possible BP monitoring texts (either daily or weekly) completed for each subject will be calculated and the proportion and 95% confidence interval will be reported by intervention group.

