We will work to prevent missing data by the recruitment and retention strategies described elsewhere. The amount and patterns of missing data and its associations with other variables (in particular intervention category) will be explored so that an appropriate statistical method for analysis can be used. If the data is missing at random (missing outcomes can be predicted from other observed variables, especially recent self-reported blood pressures), which we believe to be the most likely, since we obtain text messaging-based BPs at least weekly, the repeated measurements within individuals will allow us to use multiple imputation to handle sporadic missing at random BP measurements. For multiple imputation, we will use R package mice to impute the data using multiple imputation by chained equations. Non-normal continuous missing variables will be transformed for normality and back-transformed for any calculations necessary (e.g., change in BP). The imputation model will include all variables in the analysis model, treatment interactions, as well as other covariates that predict the missing variable and whether the missing variable is missing. Thus, associations between baseline variables and missing variables will be assessed both for strength of association and functional form. We will use 100*fraction of incomplete cases number of imputations. Analyses will combine regression estimates using Rubin's rules. Model checking will be performed on each imputed dataset through residual analysis to identify any issues with the imputation model or analysis model. Problems occurring in a small number of imputed datasets suggest a problem with the imputation dataset and problems occurring consistently across all imputed datasets suggest a problem with the analysis model.

In the case of non-ignorable missing (missing not at random) data, sensitivity analyses will be performed using pattern mixture or selection models to evaluate the robustness of our conclusions to a range of sensible conditions (for both the primary and additional analyses of the primary endpoint).

Interpretation:

Results will be reported as parameter estimates, 95% confidence intervals, and 2-sided p-values. As the goal of this exploratory trial is to find interventions and combinations with activity, we will use an alpha level of 0.10 for all main effects. Plots of mean BP levels over time will be generated for the 3 main effects and each intervention group.

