 - This binary endpoint will be assessed using logistic regression. The main predictor of interest for these models is assignment to the active primary care provider scheduling and transportation arm (50% of all subjects randomized in the trial), while adjusting for the assignment into other groups (healthy behavior text messages and prompted BP self-monitoring). We will control for age, sex, previous use of antihypertensives, and race. The interactions of these baseline variables will be assessed. Hosmer-Lemeshow Chi-Squared test will assess the goodness of fit.

(c) Since the goal of this exploratory trial is to find interventions and combinations with activity, multiple comparisons will not be controlled.

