2.7 Exploratory analyses

Endpoints:

BP

- Proportion of subjects achieving BP control (control = 6/12 month BPs are achieving target recommendations as defined by JNC8)
 - JNC-8 targets for SBP/DBP
 - 2017 AHA guidelines targets for SBP/DBP
- Change in DBP and mean arterial pressure
- Change in 6 month SBP

Process

- Number of interactions (such as calls/texts) to schedule subject initial primary care visit
- Number of interactions to schedule all other primary care visits
- Proportion of BPs texted to the study team
- Proportion enrolled but not randomized

PCP

- Establishment of a primary care providers among those without
- Self-reported number and proportion of provider visits attended
- Proportion of transportation vouchers used

Utilization

- Frequency of Hurley ED and other healthcare visits
- Self-reported follow up of emergency department visits
- Self-reported follow up of provider or clinic visits

Medications

- Changes/escalation in antihypertensive regimen through patient self-report
- Medication Adherence (Hill-Bone Scale, and modified Hill-Bone instrument asking, “How often do you forget to take your HBP medicine?”)

Other

- Social Cognitive Theory (SCT) measures
 - Modified one-question self-efficacy measure, “I am confident that I can take my blood pressure and text it to the Reach Out Team”)
 - Questions querying self-efficacy, motivation, social support and expertise.
 - I am confident that I can control my blood pressure
 - It is worthwhile for me to control my blood pressure
 - My friends and family care if I control my blood pressure
 - I know the right steps to take to control my blood pressure

Methods/Approach:

We will similarly assess the impact of the intervention components on the exploratory and process outcomes using linear, Poisson, logistic, or ordinal regression depending on the distributions. The main effects will be

tested at the $p=0.1$ level adjusting for age, sex, previous antihypertensive use, and race. Treatment interactions will be explored at the 0.2 level.

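### SAP 2.7 names Poisson as the only count model for exploratory endpoints, with no provision for over-dispersion or unequal observation time

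*SAP*

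**What the plan says.** SAP 2.7 lists the exploratory endpoints and says that the effect of the components on them will be assessed "using linear, Poisson, logistic, or ordinal regression depending on the distributions". Protocol 9.1 gives the same four families. Several endpoints are counts per person: "Frequency of Hurley ED and other healthcare visits", the number of provider visits attended, and the number of contacts needed to schedule visits. One is a proportion: "Proportion of BPs texted to the study team".

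Main effects are to be "tested at the $p=0.1$ level adjusting for age, sex, previous antihypertensive use, and race", and "Treatment interactions will be explored at the 0.2 level". SAP 2.5(c) adds that "multiple comparisons will not be controlled", because the trial is exploratory.

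SAP 2.7 assigns no model to any endpoint and names no variance estimator, dispersion parameter or offset. On texting, SAP 2.3 is more definite: "The proportion of all possible BP monitoring texts (either daily or weekly) completed for each subject will be calculated", and the result is reported by intervention group.

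**The concern.** Ordinary Poisson regression fixes the variance at the mean. Healthcare visits and scheduling contacts often vary more than that, because people differ in how much care they use. The protocol itself gives one source of spread: under section 6.1.3, facilitated appointments run about monthly until BP control and about every three months afterwards, so the number of contacts depends on each person's course.

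If the variance exceeds the mean, the model-based standard error is too small by the square root of the variance/mean ratio. Intervals are then too narrow and p-values too low. Since multiplicity is left uncontrolled, the nominal 0.10 and 0.20 levels are the only error control on these tests.

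Observation time is a second gap. Some visit counts in SAP 2.7 are self-reported, so they are complete only for people who keep answering. The plan expected 50% loss by the 12-month visit. After retention at 6 months fell short, Protocol 9.3 raised the maximum number randomized by 50% and kept the target of 240 completers. That is 480 × 1.5 = 720 at most, so as few as 240/720 = one third might complete. A count model without an exposure term reads shorter observation as fewer visits.

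At stake is how far the reported component effects on utilization and process can be trusted.

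**Working it through.** **The plan's own figures.** The documents give no power, mean, variance or dispersion for any endpoint in SAP 2.7, so there is no figure of theirs to reproduce on this point. The nearest is the 87% power for attending two or more primary care visits (40% vs 60%, 120 per group, two-sided 0.05). The normal approximation with pooled variance under the null gives 0.877, so that figure reproduces. It concerns a binary endpoint and does not bear on counts.

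**Inputs.**
- Levels: 0.10 for main effects and 0.20 for interactions (SAP 2.7).
- Sidedness: two-sided, assumed by extension from SAP 2.4 ("Results will be reported as parameter estimates, 95% confidence intervals, and 2-sided p-values").
- Sample: 240 completers in a balanced 2x2x2 layout (SAP section 1).
- φ, the variance/mean ratio that remains after the model covariates: not in the documents, assumed 1 to 5.

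**Formula.** If the true variance is φ times the model variance, a nominal two-sided test has

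true size = 2 × [1 − Φ(z/√φ)], with z = 1.645 at 0.10 and z = 1.282 at 0.20.

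Example at φ = 2: 1.645/1.414 = 1.163, and 2 × [1 − Φ(1.163)] = 0.245.

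| φ (assumed) | True size at nominal 0.10 | True size at nominal 0.20 |
|---|---|---|
| 1 | 0.100 | 0.20 |
| 1.5 | 0.179 | 0.30 |
| 2 | 0.245 | 0.36 |
| 3 | 0.342 | 0.46 |
| 5 | 0.462 | – |

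**Simulation check for counts.** No true effects, N = 240, three main effects without baseline covariates, Poisson (φ = 1) or gamma-Poisson counts, 1,500 runs, nominal 0.10. The simulation error near 0.10 is √(0.1 × 0.9/1500) ≈ 0.008.

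| Mean | φ | Ordinary Poisson | Quasi-Poisson | Poisson, robust variance |
|---|---|---|---|---|
| 1 | 1 | 0.108 | 0.111 | 0.115 |
| 1 | 1.5 | 0.166 | 0.094 | 0.097 |
| 1 | 2 | 0.251 | 0.105 | 0.106 |
| 2 | 3 | 0.348 | 0.105 | 0.109 |
| 4 | 3 | 0.335 | 0.101 | 0.102 |
| 2 | 4 | 0.394 | 0.110 | 0.113 |

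The formula and the simulation agree. Either corrected variance keeps the level close to 0.10 at every ratio tried.

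**Texting proportion.** Replies were simulated with mean 0.47 (the church pilot's 587/1248, Protocol 2.2.1), about 52 prompts per person in the weekly groups and 365 in the daily groups, and assumed within-person correlations of 0.05, 0.1 and 0.3 (800 runs each). Linear regression on one proportion per subject, as formed in SAP 2.3, rejected in 0.094 to 0.118 of runs at nominal 0.10. So the per-subject analysis holds its level.

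**The case against.** The strongest reply is that silence is not a commitment. SAP 2.7 names families, not variance estimators. SAP 2.1 examines distributions beforehand, and SAP 2.2 asks whether changes to the plan are needed. An analyst who saw over-dispersion could add a robust variance, or use linear or ordinal regression, which do not tie the variance to the mean. This stands in part: the plan does not say that over-dispersion will be ignored. But choosing by distribution among these four families leads a count to Poisson, and the list offers no other count model. Elsewhere the SAP does name its checks: AIC and BIC for covariance structure, Schoenfeld residuals for the Cox model, and Hosmer-Lemeshow for logistic regression. For counts it names none.

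Second, the degree of over-dispersion is assumed. This stands. The schedule's row on ED user status is undefined and is no evidence of heavy users.

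Third, follow-up is a fixed 12 months, and Protocol section 4 also draws on system-level data from the ED and clinics. Missing an outcome visit therefore does not by itself shorten observation of Hurley ED visits. This too stands, and it limits the offset to endpoints where observation time really differs.

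Two stronger readings are tempting. A reader might infer that individual texting prompts will be pooled in logistic regression as if independent, with very large inflation. The documents do not support this: SAP 2.3 forms one value per subject, linear regression on it is on the list, and where individual BP requests are modelled (the holiday-card sub-study, Protocol Appendix I) a random intercept is included. A reader might also infer that inflated tests here could put the wrong components into the next trial. But SAP section 1 and Protocol 9.1 select components on the systolic BP model alone.

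**Conclusion.** The point holds for counts, conditionally. With Poisson as the only count model and no allowance for over-dispersion, tests at nominal 0.10 would have a true size of about 0.18, 0.245 or 0.34 if the variance/mean ratio were 1.5, 2 or 3, and 0.10 if it were 1. Those ratios are assumptions, and excess variance is plausible but not quantified in the documents. The figures also assume that the ordinary Poisson variance is used, which the SAP neither states nor rules out. The observation-time gap applies to counts whose completeness depends on continued participation.

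For texting, all that is missing is a sentence linking SAP 2.7 to the per-subject proportion in 2.3. Severity is minor: exploratory and process endpoints are affected, and the primary, secondary and component-selection analyses are not.

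**What to change.** In SAP 2.7, and in the matching sentence of Protocol 9.1:

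1. For count endpoints, specify negative binomial regression, or Poisson regression with robust (sandwich) variance, and say which applies to which endpoint. Include log observed follow-up time as an offset where observation time differs between participants, and define that time for each data source (self-report or medical record).
2. For the proportion of BPs texted, state that the per-subject proportion of SAP 2.3 is the unit of analysis, in a linear or fractional model with robust errors. Robust errors are useful because the daily and weekly groups have very different denominators.

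This changes SAP wording only and needs no new data. Relative to ordinary Poisson, intervals for counts widen by about √φ, the factor by which they were too narrow: 1.22 at a ratio of 1.5 and 1.41 at 2, with almost no change at 1.

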Incentive	X											X						X	
Cognitive screen	X																		
ED Measured BPs	X																		
Competence w/BP cuff	X					X													
Competence with text messaging	X					X													
ASSESSMENTS:																			
Contact Information	X											X						X	
Demographics	X																		
Medical History	X																		
Tobacco/ Alcohol	X																		
Insurance Status	X																		
Transportation	X																		
SCT measures	X											X						X	
Self- efficacy modified						X	X	X	X	X		X	X	X	X	X	X		
SCT modified	X											X						X	
Self- reported BP measurement		X	X	X															
Study taken BP measurement	X											X						X	
PCP:																			
PCP	X											X						X	
First PCP visit time												X						X	
PCP attendance	X					X	X	X	X	X	X	X	X	X	X	X	X	X	

Reach Out ED
Version 14.0
1 August 2022

BP medication adherence will be assessed using several different methods: 1) Hill-Bone and one-question modified Hill-Bone question; 2) pharmacy and provider notes; 3) text participants to message pictures of their medication prior to the 6 and 12 month follow-ups. We will also ask participants to bring their medication to the 6 and 12 month follow-ups. For participants that have not done either, they will be reminded at the follow-up appointments, and texted once more afterwards. In an attempt to further monitor medication adherence, we will look for medication fill rates within the Hurley EHR, and Hamilton pharmacy records, and if there are linkages to commercial pharmacy, we will scan electronic record to assess. We will evaluate the impact of the interventions, and a brief survey regarding participant feedback on the specific intervention components they received (will be added in a future amendment).

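### SAP 2.7 analyses the Social Cognitive Theory items and medication adherence without their baseline scores, giving up some efficiency in exploratory comparisons

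*SAP*

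**What the plan says.** SAP 2.7 fits its exploratory outcomes by "linear, Poisson, logistic, or ordinal regression depending on the distributions", tests main effects at the 0.1 level and names the covariates: "adjusting for age, sex, previous antihypertensive use, and race". No baseline value of the outcome is among them.

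The outcome list mixes two forms. Blood pressure outcomes are written as changes, for example "Change in DBP and mean arterial pressure". The two groups at issue are written without any reference to change: "Medication Adherence (Hill-Bone Scale, and modified Hill-Bone instrument asking" (followed by the question on forgetting medicine) and "Social Cognitive Theory (SCT) measures".

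SAP 2.3 puts "Social Cognitive Theory Measures, medication history, medication adherence" among the baseline characteristics to be tabulated. The schedule of measures in Protocol 7.2 marks the SCT measures and the modified SCT items at baseline, 6 months and 12 months. Its row "Self- efficacy modified" is different: the first mark is at week 6, after randomization, and there is none at baseline.

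Protocol 9.1 gives the same regression families and also puts no baseline adherence or SCT score into the models.

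**The concern.** A participant's baseline score on an instrument is usually among the best predictors of the later score on that instrument. If it has been collected and is left out of the model, the variation it would have explained stays in the residual. Chance differences in baseline score between the levels of a component then remain in the estimate and are covered only by a larger standard error.

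This matters somewhat here because completers are scarce. The plan allows for 50% loss after randomization, and Protocol 9.3 reports lower retention at 6 months than expected. Some of these outcomes also bear on how the components are meant to work: Protocol Table 1 gives better medication adherence as a mechanism for the texts, and activation, autonomy and competence for self-monitoring.

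What is at stake is the precision of exploratory, mechanism-type comparisons, and nothing beyond that.

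**Working it through.** **Inputs from the documents**
- Alpha: "we will use an alpha level of 0.10 for all main effects" in SAP 2.4, with two-sided p-values; SAP 2.7 uses the same level.
- Completers: 240, from 480 randomized with 50% loss (SAP 1, Sample Size).
- Allocation: half of the participants at each level of a component, so 120 against 120.

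**Inputs that are assumptions**
- Effect size d = 0.35. This is the plan's figure for systolic BP. Protocol 9.3 ties it to 1 mm Hg over an SD of 2.8 mm Hg (1/2.8 = 0.357). The documents give none for adherence or SCT, so it is borrowed for illustration.
- Baseline-to-follow-up correlation rho. The documents give none; 0.3 to 0.7 is shown.

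**Reproducing the plan's figure.** For one two-level factor the noncentrality is d × sqrt(N)/2. With d = 1/2.8, two-sided alpha 0.10 and 80% power, the noncentral F calculation gives N = 196, the stated number. With d rounded to 0.35 it gives 204, and N = 196 has 78.7% power. The method therefore matches the plan's.

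**Adding the baseline score (linear regression).** Residual variance is multiplied by 1 − rho² and the standard error by sqrt(1 − rho²), so

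noncentrality = d × sqrt(N) / (2 × sqrt(1 − rho²)).

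With d = 0.35 and N = 240, the value without baseline is 0.35 × 15.49/2 = 2.711. Degrees of freedom are 240 − 8 = 232.

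| rho | SE factor | Noncentrality | Power | Unadjusted N of equal precision, 240/(1 − rho²) |
|---|---|---|---|---|
| no baseline | 1 | 2.711 | 85.5% | 240 |
| 0.3 | 0.954 | 2.842 | 88.3% | 264 |
| 0.5 | 0.866 | 3.130 | 93.0% | 320 |
| 0.7 | 0.714 | 3.796 | 98.4% | 471 |

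At rho 0.4 power is 90.4%, so below about 0.4 the gain is under 5 points. The degree of freedom spent is repaid once |rho| exceeds sqrt(1/232) ≈ 0.07.

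**Adherence.** Participants not on BP medicine at baseline may have no baseline score. If half have one, the factor at rho 0.5 is sqrt(1 − 0.5 × 0.25) = 0.935 rather than 0.866. The number with a follow-up score may also be below 240.

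**Logistic and ordinal models.** The table does not carry over. Adding a prognostic covariate changes the target to a conditional odds ratio, and its standard error rises. In a simulation with 240 participants and latent rho 0.5 (assumed), the standard error of the log odds ratio went from 0.26 to 0.29 in the logistic model and from 0.232 to 0.239 in the ordinal model. Ordinal power still rose, because the conditional effect grows by more than its standard error.

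**The case against.** **SAP 2.7 says it will assess these outcomes similarly, and the primary model uses a change from baseline.** A reader might infer either that baseline is already used, or that it certainly is not. The text settles neither: some outcomes are labelled as changes, these are not, and no definition is given. Both readings lead to the same fix. A change score has SD factor sqrt(2(1 − rho)), which at rho 0.3 gives about 74% power against 85.5% with no baseline. It only breaks even at rho 0.5, and it is less efficient than covariate adjustment for any rho below 1.

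**Not every outcome has a baseline score.** This stands. The one-item self-efficacy measure has no baseline mark. For adherence, SAP 2.3 names no instrument. Protocol 6.1.1 tailors texts on adherence level, so some baseline measure is likely, but a baseline on both the full Hill-Bone and the one-item version is not established.

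**Table 1 does not make self-efficacy a mechanism.** Correct. A reader might take the self-efficacy items as a test of how the texts work, but Table 1 lists self-efficacy as a tailoring variable.

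**Omitting the baseline does not widen every interval.** Correct. That inference holds for linear models only. Many of these outcomes are single agreement items that may well be fitted by ordinal or logistic regression.

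**Follow-up adherence is itself selected.** This stands too. Someone on no BP medicine at follow-up may have no score, and starting medicine is something the components may influence. Baseline adjustment does not cure that.

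**The outcomes are exploratory.** Agreed. Multiplicity is not controlled, components advance on systolic BP, and randomization keeps the unadjusted linear comparison unbiased, with a standard error that already allows for chance imbalance.

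**Conclusion.** The omission is real and its consequence is small: lost efficiency in exploratory comparisons of the SCT items marked at baseline, and of adherence where a baseline score exists. It is an optional improvement.

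For linear models the loss in power is about 3 points at rho 0.3, 7.5 at 0.5 and 13 at 0.7. This rests on an assumed rho, an effect size borrowed from systolic BP, and 240 participants with a follow-up score. The direction is firmer than the size, since almost any positive correlation repays the extra term. Adherence gains less.

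A reader might conclude that the exploratory results would be biased, or that the choice of components for the next trial is at risk. The documents support neither.

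**What to change.** Add to SAP 2.7, before these outcomes are analysed: *For each exploratory outcome that has a baseline measurement of the same instrument, the baseline score will be included as a covariate in addition to those already listed.* In linear models this also removes the level-or-change ambiguity, because both then give the same component estimate.

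The sentence covers the SCT items marked at baseline, and Hill-Bone or its one-item version where a baseline score was taken. It leaves out the one-item self-efficacy measure unless a baseline value exists.

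For adherence, set a baseline score that is missing because the participant was not on medication to a constant, and add an indicator. This retains only participants who have a follow-up score. Because being on medication at follow-up is determined after randomization, label the result as conditional on it, or also show it among participants on medication at baseline.

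The cost is one sentence and one extra term per outcome, with no new data. For adherence there is also the indicator, which will largely overlap with the existing antihypertensive covariate.
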